2.3. Sample Size

Study agreement analyses will be done per joint. To give a kappa ≥ 0.61 (from substantial interrater agreement to almost perfect agreement) with a confidence interval width of 0.15 and the expectation of approximately 20 % of joints assessed having any synovitis in B mode (based on a previous study by our group), 683 joints would be required.⁴ This corresponds to 30 patients if 24 joints per patient are assessed. Non-inferiority margin will be $\kappa \geq 0.61$.

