5.1. Outcome Definition

5.1.1. Primary Outcome

After the imaging of all patients is completed, intraarticular synovitis scoring will be done based on the OMERACT definitions (scales of 0-3) as follows, for the anatomical sites given in Table 1.^{5,6}

Greyscale inflammatory (hypoechoic) synovial hyperplasia:

Grade 0: no hypoechoic synovial hyperplasia

Grade 1: minimal hypoechoic synovial hyperplasia (filling the angle between the periarticular bones, without bulging over the line linking tops of the bones)

Grade 2: hypoechoic synovial hyperplasia bulging over the line linking tops of the periarticular bones but without extension along the bone diaphysis

Grade 3: hypoechoic synovial hyperplasia bulging over the line linking tops of the periarticular bones and with extension to at least one of the bone diaphysis

Table-1:Probes/scanners, views and anatomical sites for primary outcomes

Anatomical site	Views	GE Logic E9/S8	Clarius L15	Clarius L20
2nd MCP joints	dorsal and lateral	X	X	X
3rd MCP joints	dorsal	X		X
2nd-3rd PIP, 2nd-3rd DIP	dorsal	X		X
Wrist	dorsal	X	X	X
5th MTP joints	dorsal and lateral	X		X
Elbow joints	posterior	X	X	
Shoulder joints	posterior	X	X	
Knee joints	anterosuperior	X	X	
Ankle joints	anterior	X	X	

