5.2. Analysis Methods

Demographic, clinical and disease characteristics of patients will be presented using descriptive statistics. Numeric data showing normal distribution will be shared with mean and standard deviation, and those without normal distribution will be shared with median and interquartile range. Categorical data will be shared with numbers and percentages.

The primary endpoint analysis will be the interrater agreement of detecting any synovitis in B mode with the Clarius and gold standard machine. The kappa coefficients will be evaluated using the guideline outlined by Landis and Koch, where the strength of the kappa coefficients are: 0.01-0.20 slight; 0.21-0.40 fair; 0.41-0.60 moderate; 0.61-0.80 substantial; 0.81-1.00 almost perfect.⁷

For secondary outcomes, the interrater agreement for the presence of Doppler signals within the joints, tenosynovitis, erosions, nail, as well as features of enthesitis (hypoechoicity, thickening, erosions, enthesophytes, calcifications) will also be evaluated using the same method. The agreement of the semiquantitative grading of the intraarticular findings' severity (synovitis in B mode, Doppler signals, erosions, each being on a scale between 0-3) will be done using weighted kappa analysis.⁸

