5.3. Missing Data

If there are missing images for some sites for any of the probes, the images that were obtained for the same site using other probe(s) will also be excluded. The number of missing joint/tendon/enthesis and nail images will be reported. Missing data will not be imputed.

6. References

2-Filer A, de Pablo P, Allen G, Nightingale P, Jordan A, Jobanputra P, Bowman S, Buckley CD, Raza K. Utility of ultrasound joint counts in the prediction of rheumatoid arthritis in patients with very early synovitis. *Ann Rheum Dis*. 2011 Mar;70(3):500-7. doi: 10.1136/ard.2010.131573. Epub 2010 Nov 29. PMID: 21115552; PMCID: PMC3033529.

8-Cohen J, Weighed kappa: Nominal scale agreement with provision for scaled disagreement or partial credit. *Psychological Bulletin*.1968, 70 (4): 213–220

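### SAP 5.3 deletes a joint from every device when any probe's image is missing, so the primary kappa is conditional on imaging success and no planned analysis shows what handheld failures would do to the 0.61 claim

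*SAP*

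**What the plan says.** The primary objective (Protocol section 3.0, SAP section 1.2) asks whether the handheld scanners are as accurate as the GE device at visualising synovitis in B mode. SAP section 5.2 makes this a kappa: "The primary endpoint analysis will be the interrater agreement of detecting any synovitis in B mode with the Clarius and gold standard machine". The sample-size sections (Protocol 4.5, SAP 2.3) set the criterion at kappa of at least 0.61.

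SAP section 5.3 governs missing images. The trigger is "If there are missing images for some sites for any of the probes", and the consequence is that "the images that were obtained for the same site using other probe(s) will also be excluded". It adds "Missing data will not be imputed" and "The number of missing joint/tendon/enthesis and nail images will be reported". The rule is symmetric, so a missing GE image also removes the handheld image. The count is described by type of structure; a breakdown by device, probe or reason is not stated. No sensitivity analysis appears in either document.

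The synovitis scale (Protocol 4.3, SAP 5.1.1) starts at "Grade 0: no hypoechoic synovial hyperplasia" and ends at grade 3. It has no code for an image that was saved but cannot be read, and neither document says how such an image is handled. Protocol 4.3 and SAP 2.2 acknowledge that the central reader can tell which machine produced an image.

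**The concern.** In a device-validation study, failure to produce a usable image is part of the device's performance. A clinician whose handheld gives no view of a joint has not detected synovitis there. Under section 5.3 that joint leaves the analysis on both devices. The reported kappa then answers how well the handheld agrees with GE where all assigned probes gave an image. The objective is wider than that.

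At stake is the 0.61 claim. If the observed kappa lies somewhat above 0.61, a modest number of handheld failures could decide whether the claim also holds for the joints the study set out to image. The planned output would not reveal this: there is no second analysis, and a count that does not separate handheld from GE failures does not let a reader rebuild one.

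The lack of a rule for unreadable images adds to this. Each one is left to the judgement of a reader who can see which machine it came from, and the choice would not be recorded.

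**Working it through.** **1. The plan's own figure.** Inputs from SAP 2.3 and 3.1: kappa k = 0.61, prevalence p = 0.20, 95% confidence interval of full width 0.15. The large-sample variance for a binary kappa with equal margins is

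n·Var = (1−k)·[(1−k)(1−2k) + k(2−k)/(2p(1−p))] = 0.39 × [−0.0858 + 2.6497] = 0.9999.

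N = 4 × 1.96² × 0.9999 / 0.15² = 682.87, rounded up to 683. The stated figure reproduces. The planned 30 × 24 = 720 joints leave 37 spare (5.1%). At 5% loss the interval width is 0.150 and at 10% it is 0.154. Precision is therefore not the issue; what matters is which joints the kappa describes.

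**2. Counting handheld failures as not detected.** Assumptions, since the documents give no failure rate:
- 720 joints with 144 GE-positive (20%), and one handheld reading per joint
- kappa 0.65 among evaluable pairs, with equal margins
- failure in 3%, 5% or 10% of joints
- failed joints either 20% or 50% GE-positive.

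With n evaluable joints and GE-positive share r among them, each discordant cell is n·r(1−r)(1−0.65). Failed joints are then added as handheld-negative and kappa = (po − pe)/(1 − pe) is recomputed.

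Example, 5% failure with half of the failed joints GE-positive:
- 36 joints fail, 18 of them GE-positive, leaving n = 684 with 126 GE-positive (r = 0.1842).
- Each discordant cell is 684 × 0.1842 × 0.8158 × 0.35 = 35.98. Both positive: 90.02. Both negative: 522.02. Kappa = 0.65.
- Adding the failures, GE-positive/handheld-negative becomes 53.98 and both negative becomes 540.02.
- po = (90.02 + 540.02)/720 = 0.8751. Handheld-positive share = 126/720 = 0.175. pe = 0.20 × 0.175 + 0.80 × 0.825 = 0.695.
- Kappa = (0.8751 − 0.695)/0.305 = 0.590.

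| Handheld failure | Kappa under deletion | Not detected, failed joints 20% GE-positive | Not detected, failed joints 50% GE-positive |
|---|---|---|---|
| 3% | 0.65 | 0.638 | 0.615 |
| 5% | 0.65 | 0.629 | 0.590 |
| 10% | 0.65 | 0.608 | 0.526 |

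Three of the six results fall below 0.61. The deletion column is constant because 0.65 was fixed as the starting point; it is an input and not a finding.

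**3. Direction of the bias from deletion.** Suppose the kappa with all images present would be 0.58 at 20% prevalence, and 10% of joints are lost. Each discordant cell is 0.16 × 0.42 = 0.0672 of joints.

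| Which joints fail more often | Kappa after deletion | Change |
|---|---|---|
| None (random) | 0.580 | 0.00 |
| Discordant joints, 3 times as often | 0.634 | +0.05 |
| Joints the handheld would miss, 3 times as often | 0.610 | +0.03 |
| GE-positive joints, 3 times as often | 0.566 | −0.01 |
| Joints positive on both devices, 3 times as often | 0.537 | −0.04 |

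Deletion can lift a kappa from below to above 0.61, but only under particular mechanisms.

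**4. Unreadable images scored as grade 0.** For the binary endpoint, grade 0 is handheld-negative, so this is the same calculation as step 2 and gives values below 0.65. Kappa rises only if almost no failed joint is GE-positive. With none GE-positive it is 0.653, 0.655 and 0.660 at 3%, 5% and 10% failure, a gain of at most 0.01.

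All of these are joint-level point estimates. They ignore clustering of joints within patients, as the plan's own sample size does.

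**The case against.** The strongest reply is that section 5.3 is an ordinary complete-pair rule. It treats all devices alike, concerns missing images without mentioning device failure, and discloses losses through a count. Protocol 4.3 requires at least one B-mode and one Doppler image per site, and Protocol 8.0 has uploads checked centrally with sites contacted about missing data, so few images may be lost. All the failure rates above are assumed. This stands, and it rules out saying that the primary kappa is biased. It does not supply an analysis showing whether the claim survives handheld failures, and the count as described need not distinguish them from GE failures.

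A reader might infer more: that unreadable handheld images will be scored as normal, that a normal score agrees with GE in about 80% of joints, and that this inflates kappa. The documents do not support this. They do not say how unreadable images are scored, and a reader could equally treat them as missing. Kappa also corrects for chance agreement, and step 4 shows that scoring failures as grade 0 normally lowers it. A grade 0 on a GE-positive joint does count against the handheld.

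A harsher bound would count every failed joint as discordant, giving about 0.58 at 3% failure, 0.53 to 0.54 at 5% and 0.41 to 0.44 at 10%. That makes failed GE-negative joints into handheld false positives, which a missing image cannot be. It is an extreme limit and should not drive the conclusion.

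**Conclusion.** The point holds as a matter of what is estimated and of a missing sensitivity analysis. The primary kappa is conditional on every assigned probe having produced an image, and under section 5.3 a handheld failure at a joint that GE imaged never counts against the handheld. Deletion may favour the handheld if failures fall mainly on joints that would have disagreed. It has no effect if failure is random and can work against the handheld under other patterns, so a bias in its favour is a risk and not an established fact.

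The size is enough to matter near the criterion. From an assumed 0.65, counting failures as not detected crosses 0.61 at 5% failure if half of the failed joints are GE-positive, and at 10% failure even if only 20% are. At 3% it does not cross. This rests on assumed failure rates, an assumed kappa among evaluable pairs, and comparison of the point estimate with 0.61. The plan should be changed on this point, but the defect does not invalidate the design.

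**What to change.** 1. Add a not-assessable code for the central reader to the reading form.
2. Report missing and not-assessable images by device, probe, anatomical site and reason, beside the kappa.
3. In SAP 5.3, pre-specify one sensitivity analysis of the primary kappa in which joints readable on GE but missing or not assessable on the handheld count as handheld-negative. Report it next to the primary kappa and use it in interpreting the 0.61 claim. It need not be a second success criterion.
4. Optionally add the fully discordant version, labelled as an extreme worst case.

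The cost is one extra code and one extra run of the same analysis. The downside is that the additional figure may be slightly less favourable to the handheld.
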